## **9.2 Reader Set Sample Size**

This Imagio Feasibility Study is not powered but should be more than adequate to estimate effect sizes to power the subsequent pivotal study.

Every effort will be made to identify missing reads and to provide readers with the opportunity to read all 155 image sets which includes the two additional cohorts:

- Cohort 1: 120 masses (75 benign, 45 malignant) to represent the PIONEER study
- Cohort 2: 30 additional malignant masses with FNs
- Cohort 3: 5 DCIS, lymphoma and phyllodes masses.

All reads will be included in all analyses, consistent with an “intention to diagnose” approach.

## **9.4 Population Definition**

The original PIONEER Intention-to-diagnose classification will be used. Images will be selected for use in accordance with the study protocol inclusion and exclusion criteria.

## **9.5 Interim Analyses**

An interim analysis of the data is planned to follow a completion of a minimum of 72 completed Cohort 1 mass reads by each reader in Part 2 to assess intermediate performance results.

## **9.6 Protocol Deviations**

The study data will be evaluated for major and minor protocol deviations. This will be limited to missing and incomplete reads from the Feasibility Study.

At study completion, the number and type of protocol deviations will be analyzed by the study biostatistician to review the events by reader to determine whether there are statistical concerns. The biostatistician will report findings to the study sponsor.

The findings will be used to improve the pivotal study design in the event that the pivotal study is to proceed.

## **9.7 Outcomes**

Outcomes will be analyzed according to the PIONEER Truth Panel findings and the pathology diagnosis (if available) as truth; Truth Panel Benign (TPB) will be a benign diagnosis. The final analyses will be performed following database lock.

## **9.8 Data Analyses**

All analyses will be performed in a GCP-controlled environment using SAS v9.3 or higher and StatXact v10 or later unless otherwise specified.

All significance testing will be two-sided; results will be presented using two-sided p-values and two-sided 95% confidence intervals. All p-values are considered to be descriptive.

Methods of analysis for the MRMC design will be analyzed treating readers as random effects and treatment and masses as fixed effects and also by MRMC analysis methods by Obuchowski and Rockette where both reader and mass are random effects (see references). Two-sided 95% confidence intervals will be computed for the Imagio (IUS+OA) as well as Imagio (IUS+OA) - versus IUS differences in ROC AUC and the differences in downgrade and upgrade percentages separately for benign and malignant masses. The same analyses will be performed for the SenoGram versus IUS and versus Imagio (IUS+OA). These outcomes will be used to guide decisions regarding pivotal study design.

For each endpoint, Cohort 1 subgroup analyses will be performed in the same manner for those with a prior mammogram as well as for those without a prior mammogram.

#### 1. Sensitivity, Specificity, Partial ROC AUC, and Specificity for Fixed Sensitivity

Individual reader specificity and sensitivity will be calculated from simple counts for POMs to construct the respective ROC curves for IUS, the Imagio (IUS+OA) and the SenoGram. GEE and ANOVA will be used to describe overall specificity and sensitivity as well as to compute the two-sided 95% confidence intervals for the OA-IUS differences for sensitivity and for specificity.

The specificity advantage for fixed sensitivity will be the primary endpoint. It will be computed from the respective ROC curves which are generated according to the POMs corresponding to the 95-99% sensitivity range. To compute the specificity advantage for fixed sensitivity, interpolation may be required; a fixed sensitivity will be targeted, e.g., 98%. To compute the specificity advantage and the partial area under the ROC, the specificities and sensitivities may need to be further computed from the ROC curves as needed. The McClish method will be used to analyze and compare the partial ROC curves. The variances will be computed to construct the two-sided 95% CIs for Imagio (IUS+OA), IUS, and for the Imagio (IUS+OA) -IUS difference. The same analyses will be performed for the SenoGram versus IUS and versus Imagio (IUS+OA).

In addition, the interpolation and the corresponding variance estimate will also permit the calculation of the specificity difference for fixed sensitivity (e.g. 98%) as well as the two-sided 95% confidence interval for the difference.

#### 2. Upgrades and Downgrades

Separately for benign + TPB masses and malignant masses, downgrades and upgrades will be jointly assessed for each diagnostic category using a McNemar paired comparison test for Imagio (IUS+OA) versus IUS. In addition, two-sided 95% confidence intervals will be computed for the OA-IUS differences for both specificity and sensitivity; superiority will be sought for specificity while non-inferiority will be sought for sensitivity. Refer to Table 1 below.

**Table 1: Upgrades and Downgrades**

	Imagio (IUS+OA) Clinical Significance Criteria	Imagio (IUS+OA) Statistical Significance Criteria
Benign + TPB Downgrades	BR4a→BR2-3; BR3→BR2	Establish an advantage
Benign + TPB Upgrades	BR2-3→BR4-5; BR2→BR3-4-5	Rule out a disadvantage
Malignant Upgrades	BR2→BR4-5; BR3→BR4-5	Establish an advantage
Malignant Downgrades	BR4→BR2-3; BR5→BR2-3	Rule out a disadvantage

Supporting descriptive statistics will be computed as follows for the correct downgrades and incorrect upgrades for benign masses. Refer to Table 2 below.

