## 2.2 Secondary Endpoints

To evaluate the following overall and for individual readers for:

1. the partial ROC AUC corresponding to 95-99% sensitivity with specificities extrapolated from the respective Imagio and IUS ROC curves as applicable.
  - the observed and model-adjusted specificity and sensitivity
  - the Negative Likelihood Ratio (NLR) defined as  $((1-\text{sensitivity})/\text{specificity})$
  - the upgrade and downgrade metrics:
    - the percent correct of downgrades for benign masses from IUS BI-RADS 4a to Imagio (IUS+OA) BI-RADS 2-3, and from IUS BI-RADS 3 to Imagio (IUS+OA) BI-RADS 2
    - the percent incorrect of upgrades for benign masses from IUS BI-RADS 2-3 to Imagio (IUS+OA) BI-RADS 4-5 and from IUS BI-RADS 2 to Imagio (IUS+OA) BI-RADS 3-4-5
    - the percent of incorrect downgrades for malignant masses from IUS BI-RADS 4-5 to Imagio (IUS+OA) BI-RADS 2-3; and
    - the percent of correct upgrades for malignant masses from IUS BI-RADS 2-3 to Imagio (IUS+OA) BI-RADS 4-5.
2. the Cumulative effect of downgrades and upgrades for combined benign masses and malignant masses.
3. the SenoGram usage:
  - Utilization percent reported by the readers
  - Sensitivity and specificity discordance with Imagio (IUS+OA) Downgrades and upgrades versus Imagio (IUS+OA) and IUS, separately for benign and malignant masses
  - POM paired differences versus Imagio (IUS+OA) and IUS, separately for benign and malignant masses.
4. the SenoGram performance:
  - Sensitivity and specificity compared to sensitivity and specificity estimated from cross-validation and hold-out validation.
  - Partial AUC for individual users and overall corresponding to 95-99% sensitivity
  - Separate assessment of Senogram performance with and without mammographic data input.

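### The benign McNemar comparison sets upgrades against downgrades on cells that are not mirror images, which tilts it against Imagio when the two scores are exchangeable

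*Protocol*

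**What the plan says.** Protocol 9.8 item 2 states that, for benign plus Truth Panel benign masses and for malignant masses separately, "downgrades and upgrades will be jointly assessed for each diagnostic category using a McNemar paired comparison test for Imagio (IUS+OA) versus IUS". It then refers to Table 1, which sets a statistical aim beside each group of moves.

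- Benign downgrades: "BR4a→BR2-3; BR3→BR2", where the aim is to show an advantage.
- Benign upgrades: "BR2-3→BR4-5; BR2→BR3-4-5", where the aim is to exclude a disadvantage.
- Malignant upgrades: "BR2→BR4-5; BR3→BR4-5".
- Malignant downgrades: "BR4→BR2-3; BR5→BR2-3".

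Protocol 2.2 has the same benign sets: "the percent correct of downgrades for benign masses from IUS BI-RADS 4a to Imagio (IUS+OA) BI-RADS 2-3" on one side and "the percent incorrect of upgrades for benign masses from IUS BI-RADS 2-3 to Imagio (IUS+OA) BI-RADS 4-5" on the other, plus 3 to 2 and 2 to 3 or higher. Protocol 5.1 expects readers to use the BI-RADS 4 subcategories, so 4b and 4c are live categories.

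The opening of Protocol 9.8 separately plans 95% intervals for differences in downgrade and upgrade percentages, by diagnosis. SAP 1.1.7 (Table 1) and 1.1.7.1 keep the 4a-only downgrade rule, apply it to benign masses and cancers alike, and plan counts with 95% intervals without naming McNemar. SAP 1.1.7.1 defines A and B in A-B+W(C-D) as benign downgrades and upgrades. SAP section 2 does not list the absence of McNemar as a change.

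**The concern.** McNemar's test asks whether two opposite kinds of discordant pair are equally likely. That null means no difference only if each kind is the reverse of the other. The malignant rows of Table 1 meet this condition; the benign rows do not. A benign mass moving from 3 to 4b counts against Imagio, while one moving from 4b to 3 earns no credit.

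Two consequences follow. With no real difference, the comparison can lean towards a disadvantage. With a real benefit, moves from 4b, 4c or 5 down to 2-3 are left out, so the net benign gain is understated. These results are among those meant to guide the pivotal design.

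**Working it through.** **Inputs from the documents.** The cells come from Protocol Table 1. Cohort 1 has 75 benign masses (Protocol 9.2). Testing is two-sided at 5%. The documents give no rate, power or sample size for this comparison, so there is no stated figure to reproduce.

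**Step 1: list the cells** over BI-RADS 2, 3, 4a, 4b, 4c and 5.

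- Benign downgrades: 4a→2, 4a→3, 3→2 (3 cells).
- Benign upgrades: 2→3, 2→4a, 2→4b, 2→4c, 2→5, 3→4a, 3→4b, 3→4c, 3→5 (9 cells).
- All 3 downgrade cells have their reverse among the upgrades. The other 9 - 3 = 6 upgrade cells (2 or 3 to 4b, 4c or 5) have none.
- Malignant: 2-3→4-5 against 4-5→2-3, an exact mirror.

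**Step 2: expected difference with no effect.** Let p(i,j) be the probability of IUS category i and Imagio category j. If the scores are exchangeable, p(i,j) = p(j,i). The three mirrored pairs cancel, leaving

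P(up) - P(down) = P(2-3 → 4b, 4c or 5) ≥ 0.

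The sign needs no outside figure. It does need exchangeability: equal marginal distributions alone do not fix it.

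**Step 3: size, under assumptions.** A bivariate normal latent score was cut into six categories. Three benign share vectors for (2, 3, 4a, 4b, 4c, 5) were assumed:

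- 17% in 4b-5: 0.10, 0.35, 0.38, 0.10, 0.05, 0.02
- 30% in 4b-5: 0.05, 0.25, 0.40, 0.17, 0.10, 0.03
- 45% in 4b-5: 0.05, 0.20, 0.30, 0.25, 0.15, 0.05

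Each cell below gives the excess of upgrades in percentage points, then the false rejection rate against / in favour of Imagio. The rates are for one reader, 75 benign masses and McNemar without continuity correction (nominal 2.5% each way).

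| Share in 4b-5 | Correlation 0.9 | 0.8 | 0.7 | 0.5 |
|---|---|---|---|---|
| 17% | 0.04; 2.4% / 2.3% | 0.43; 3.1% / 2.2% | 1.10; 3.9% / 1.8% | 2.81; 5.9% / 1.0% |
| 30% | 0.06; 2.3% / 2.1% | 0.53; 3.1% / 1.9% | 1.32; 4.3% / 1.5% | 3.31; 7.8% / 0.7% |
| 45% | 0.26; 2.5% / 1.9% | 1.23; 4.0% / 1.3% | 2.44; 6.4% / 0.8% | 4.98; 13.7% / 0.3% |

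The two extremes:

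- 17% and 0.9: P(down) = 0.1017, P(up) = 0.1021. Expected counts are 75 × 0.1017 = 7.6 and 75 × 0.1021 = 7.7. The upgrade share of discordant pairs is 0.1021 / 0.2038 = 50.1%.
- 45% and 0.5: P(down) = 0.1006, P(up) = 0.1503. Expected counts are 7.5 and 11.3. The upgrade share is 0.1503 / 0.2509 = 59.9%.

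With the exact McNemar test the rates are lower, 1.3% to 9.2% against and 0.1% to 1.4% in favour, with the same tilt.

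**Step 4: mirrored cells.** With upgrades limited to the three reverses of the downgrade cells, the rejection rate is 2.2% to 2.7% in each direction in every scenario. Extending the downgrades to all of 4-5→2-3 restores P(up) = P(down) by the same symmetry.

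**The case against.** **The 4a restriction is deliberate.** Table 1 labels these moves as clinical significance criteria, and Protocol Table 2 reports each transition separately. That supports keeping the 4a-only percentage as a description. It does not make the set suitable for a symmetric test.

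**McNemar may be meant on 2-3 versus 4-5,** which would be symmetric. The reference to Table 1 follows the sentence on specificity and sensitivity, so some ambiguity stands. But Table 1 includes 3→2 and 2→3, which lie on one side of that cut, so this reading does not fit the table.

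**The SAP names no McNemar test.** This stands as a discrepancy. It does not remove the problem, because the SAP keeps the asymmetric sets and uses benign downgrades and upgrades as A and B. Protocol 1.2 describes net gain through new true and false positives and negatives, which would be symmetric, so A-B is affected only if the SAP definitions are the ones applied.

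**The offset may be trivial.** Read 2 follows Read 1 at once in the same session, so very high agreement is plausible. This stands.

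A reader might also infer that the specificity and sensitivity intervals in item 2 are off-centre. They are not: they compare positive and negative calls (the SAP uses a 2% POM cutoff), and the 4a rule does not enter them. A reader might infer too that the move-forward decision is distorted. The documents do not show that. P-values are descriptive, the criteria in 9.8 item 3 are illustrations, and the relevant one pairs benign downgrades with malignant upgrades rather than using a net benign McNemar result.

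**Conclusion.** The concern holds as a limited point about a descriptive secondary analysis. The mismatch of cells is plain from Table 1. Under exchangeable scores its direction is against Imagio, strictly so whenever benign masses move from 2-3 to 4b or higher.

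Its size cannot be determined from the documents. The range of about 0.04 to 5 percentage points rests on the assumed shares and correlations, and the lower end is of no practical importance. The offset applies when both percentages are taken over all benign masses. The percentages in Protocol Table 2 use different IUS denominators for downgrades and upgrades, so subtracting those is not a paired contrast in any case.

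Affected: the benign McNemar comparison, the interval for downgrade versus upgrade percentages and, under the SAP definitions, A-B in the net gain. Not affected: the primary endpoint, the specificity and sensitivity intervals, the protocol's malignant comparison, and any formal hypothesis test, since none is planned.

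**What to change.** In Protocol 9.8, state that the benign McNemar test, the downgrade-minus-upgrade difference and the A-B contrast use mirrored cells: 4-5→2-3 against 2-3→4-5, and 3→2 against 2→3. The upgrade set stays as it is; only the downgrade set used for these contrasts widens. Keep the 4a-only downgrade percentage as the descriptive figure in Table 2.

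Make the same change in SAP 1.1.7 and 1.1.7.1; editing the protocol alone would leave the SAP definitions in force. Reconcile two further points between the documents:

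- whether McNemar is run at all, with an entry in SAP section 2 if it is not;
- the SAP's use of the 4a-only downgrade definition for cancers, which conflicts with Protocol Table 1. It leaves malignant moves from 4b, 4c or 5 to 2-3 uncounted, and so leans the other way, towards Imagio, in C-D.

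The cost is some wording and one extra tabulation from data already being collected.

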**Table 2: Correct Downgrades and Incorrect Upgrades**

Imagio (IUS+OA) Outcome (IUS→Imagio)	Benign + TPB Masses
BR4a→BR3	% (IB3/IB4a)
BR4a→BR2	% (IB2/IB4a)
BR3→BR2	% (IB2/IB3)
Correct Downgrade	% (IBN/IBD)
Imagio (IUS+OA) Outcome (IUS→Imagio)	Benign + TPB Masses
BR2→BR3+	% (IB3-5/IB2)
BR3→BR4a+	% (IB4-5/IB3)
Incorrect Upgrade	% (IBN/IBD)

Supporting descriptive statistics will be computed as follows for the correct upgrades and incorrect downgrades for malignant masses. Refer to Table 3 below.

**Table 3: Correct Upgrades and Incorrect Downgrades**

Imagio (IUS+OA) Outcome (IUS→Imagio)	Malignant Masses
BR2→BR4-5	% (IC4-5/IC2)
BR3→BR4-5	% (IC4-5/IC3)
Correct Upgrades	% (ICN/ICD)
Imagio (IUS+OA) Outcome (IUS→Imagio)	Malignant Masses
BR4->BR2-3	% (IC2-3/IC4)
BR5->BR2-3	% (IC2-3/IC5)
Incorrect Downgrades	% (ICN/ICD)

To assess the cumulative effect of downgrades and upgrades for combined benign masses and malignant masses, a net gain will be computed for downgrades and upgrades. The net gain will be computed in SAS according to contrast statements for the ANOVA models to simultaneously analyze reader and mass. The weight (W) of the malignant outcomes (TP and FN) will be computed to determine the value  $(A-B+W(C-D))$  that achieves statistical significance. The same analyses will be performed for the SenoGram versus IUS and versus Imagio. Refer to Table 4 below.

**Table 4: Net Gain**

	Imagio (IUS+OA) Relative to IUS
Benign Masses Picked Up	A
Benign Masses Lost	B
Malignant Masses Picked Up	C
Malignant Masses Lost	D
Numeric Gain	A-B+C-D

### 3. Move Forward Criteria

The move forward criteria will be dependent on data from the above endpoints. As illustration, the following criteria would justify conducting the Pivotal Study:

- An Imagio (IUS+OA) specificity advantage versus IUS for fixed sensitivity;
- An Imagio (IUS+OA) specificity advantage with a minimal OA sensitivity disadvantage;
- An Imagio (IUS+OA) advantage for benign mass downgrades with a minimal Imagio (IUS+OA) disadvantage for malignant mass upgrades.

The same analyses will be performed for the SenoGram versus IUS and versus Imagio. Depending which criteria are selected for inclusion as pivotal study primary endpoints, the pivotal study will be designed to have 80% power with two-sided 5% Type I error; there are 1,757 masses available from the PIONEER Pivotal Study.

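### The third illustrative move-forward criterion limits harm on malignant upgrades, which Table 1 treats as a benefit, and omits malignant downgrades, which Table 1 treats as the harm

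*Protocol*

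**What the plan says.** Protocol 9.8 item 3 introduces its list with "As illustration, the following criteria would justify conducting the Pivotal Study". The first criterion is a specificity gain at fixed sensitivity. The second is "An Imagio (IUS+OA) specificity advantage with a minimal OA sensitivity disadvantage". The third is "An Imagio (IUS+OA) advantage for benign mass downgrades with a minimal Imagio (IUS+OA) disadvantage for malignant mass upgrades". The same item adds that the pivotal study will be powered according to which of these criteria are chosen as its primary endpoints. It does not say whether the three must be met together, and it gives no margin for 'minimal'.

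Protocol 2.2 defines the two malignant movements as secondary endpoints. The favourable one is "the percent of correct upgrades for malignant masses from IUS BI-RADS 2-3 to Imagio (IUS+OA) BI-RADS 4-5" and the unfavourable one is "the percent of incorrect downgrades for malignant masses from IUS BI-RADS 4-5 to Imagio (IUS+OA) BI-RADS 2-3". Protocol Table 1 (9.8 item 2) lists them on separate rows. Malignant upgrades ("BR2→BR4-5; BR3→BR4-5") are where an advantage is to be shown. Malignant downgrades ("BR4→BR2-3; BR5→BR2-3") are where a disadvantage is to be excluded.

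Protocol 9.1 bases the decision to proceed on the primary and secondary endpoints in Cohort 1 (75 benign, 45 malignant) taken collectively. The SAP neither restates nor corrects the move-forward criteria.

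**The concern.** The third criterion expresses the device's trade-off in BI-RADS terms: fewer benign masses worked up, against cancers missed. It names the benefit correctly, but it attaches the tolerance for harm to the movement that would be a second benefit. The movement that creates a false negative is not mentioned.

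That side of the trade-off is the one the protocol has most reason to watch. Section 4 sets up Cohort 2 because of the excess false-negative rate seen with OA in PIONEER, and 9.1 acknowledges that false negatives and false positives trade against each other. If the third criterion were carried into the pivotal study as worded, a formal endpoint could inherit a harm limit that does not measure the harm.

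**Working it through.** The plan states no figure for this point, so there is none to reproduce. The check compares wording and then illustrates the consequence.

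**Step 1. Direction of each malignant movement.**

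| Place | Malignant upgrade | Malignant downgrade |
|---|---|---|
| Protocol 2.2 | correct | incorrect |
| Protocol Table 1 | show an advantage | exclude a disadvantage |
| Protocol Table 3 | correct | incorrect |
| Protocol Table 4; SAP 1.1.7.1 net gain | C, plus sign | D, minus sign |
| Protocol 9.8 item 3, third criterion | tolerated disadvantage | not mentioned |

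The last row is the only one that departs from the pattern.

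**Step 2. Whether the upgrade figure can reflect downgrades.** Under Protocol 2.2 and Tables 1 and 3, malignant upgrades are counted among cancers that IUS placed in BI-RADS 2-3, and malignant downgrades among those it placed in 4-5. These groups do not overlap. The upgrade count is taken relative to IUS and cannot fall below zero, so on its own it has no scale on which a disadvantage could appear.

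**Step 3. How many cancers could move each way.** Input: 45 malignant masses in Cohort 1 (Protocol 4 and 9.2). Assumption: IUS sensitivity Se, taken as the share of cancers IUS places in BI-RADS 4-5.

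- Able to move up = 45 × (1 − Se); able to move down = 45 × Se.
- Se = 98%: 45 × 0.02 = 0.9 up; 45 × 0.98 = 44.1 down.
- Se = 95%: 45 × 0.05 = 2.25 up; 45 × 0.95 = 42.75 down.
- Se = 90%: 4.5 up; 40.5 down.

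**Step 4. Illustration for one reader.** Assume IUS places 44 of the 45 cancers in BI-RADS 4-5. With C upgrades and D downgrades, Imagio sensitivity = (44 − D + C)/45, against 44/45 = 97.8% for IUS.

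| C | D | Upgrades | Downgrades | Imagio sensitivity | Change (points) |
|---|---|---|---|---|---|
| 0 | 0 | 0/1 | 0/44 = 0% | 44/45 = 97.8% | 0 |
| 0 | 1 | 0/1 | 1/44 = 2.3% | 43/45 = 95.6% | −2.2 |
| 0 | 3 | 0/1 | 3/44 = 6.8% | 41/45 = 91.1% | −6.7 |
| 0 | 5 | 0/1 | 5/44 = 11.4% | 39/45 = 86.7% | −11.1 |
| 1 | 5 | 1/1 | 5/44 = 11.4% | 40/45 = 88.9% | −8.9 |
| 0 | 9 | 0/1 | 9/44 = 20.5% | 35/45 = 77.8% | −20.0 |

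With C = 0, the upgrade figure is the same whether no cancers or nine are downgraded. With C = 1 and D = 5 it looks favourable while sensitivity falls. No pass or fail point can be calculated, because 'minimal' has no margin.

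**Step 5. Whether the SAP would supply the right count.** SAP Table 1 and SAP 1.1.7.1 define a downgrade only as IUS 4a to Imagio 2-3, or 3 to 2. SAP 1.1.7.1 reports this for cancers as well as benign masses, and the Cohort 2 row of SAP Table 1 reuses it for cancers. Protocol Table 1 counts malignant moves to 2-3 from any BI-RADS 4 or 5. Cancers moved from 4b, 4c or 5 to 2-3 therefore fall outside the SAP definition. The PIONEER table layout that the SAP cites for cancers is not in the documents, so it cannot be checked whether that display would show them.

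**The case against.** A reader might infer that a device that downgrades cancers would satisfy the plan's go/no-go rule, or that these three criteria are the only basis for the decision. The documents do not support either reading. The list is offered as an illustration. Protocol 9.1 rests the decision on the endpoints collectively, and these include malignant downgrades, sensitivity, NLR and net gain with lost cancers subtracted. The second criterion limits the loss of sensitivity, the first is set at fixed sensitivity, Table 1 carries a malignant-downgrade row, and 9.8 item 2 seeks non-inferiority for sensitivity. Cohort 2 looks separately at masses missed in PIONEER. This part of the objection stands: several other elements would register downgraded cancers.

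It can also be said that the phrase means net upgrades, since 9.8 item 2 states that "downgrades and upgrades will be jointly assessed for each diagnostic category using a McNemar paired comparison test". On that reading a net loss among cancers would count as a disadvantage. But the criterion does not say net, and Table 1 lists the two movements on separate rows with different aims. The joint test makes a slip of wording the likely explanation; it does not make the wording right.

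Finally, the study is unpowered and tests no formal hypothesis, so no estimate, interval or test changes. That is correct and limits the severity. It does not remove the point: the criteria are not stated to be joint, 9.1 gives no rule for weighing endpoints that conflict, and item 3 treats the criteria as candidates for pivotal primary endpoints.

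**Conclusion.** The third criterion is wrong in direction as written. It conflicts with Protocol 2.2, Tables 1, 3 and 4 and the SAP's net-gain terms, and nothing in the SAP corrects it. Its malignant half, taken alone, does not respond to cancers moved from BI-RADS 4-5 to 2-3.

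The defect is confined to that criterion. It is an inconsistency in an illustrative decision guide, not a plan that tolerates missed cancers. It should be corrected chiefly because the wording could be carried into a pivotal endpoint.

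The 1-2 cancers of 45 able to move up and 43-44 able to move down rest on an assumed IUS sensitivity of 95-98%, and the reader illustration on an assumed 44 of 45. These figures show how little of the malignant sample the criterion observes. They do not estimate any change in the go/no-go decision. The mismatch itself depends on no assumption.

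**What to change.** In Protocol 9.8 item 3, replace malignant mass upgrades with malignant mass downgrades (BI-RADS 4-5 to 2-3), so that the criterion matches the row of Protocol Table 1 on which a disadvantage is to be excluded.

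In SAP Table 1 and SAP 1.1.7.1, give cancers their own downgrade definition, any BI-RADS 4 or 5 to 2-3, so that moves from 4b, 4c and 5 are counted in Cohorts 1 and 2. State that net-gain term D uses it.

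It would also help to say in item 3 whether the criteria apply jointly or as alternatives, and what size of disadvantage counts as minimal.

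The cost is one phrase in the protocol, a few lines in the SAP and possibly a revised table layout for cancers. BI-RADS is already recorded for both reads, so no new reads or data are needed.
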